DETAILED RESEARCH PROTOCOL

February 5, 2021

A. PURPOSE: *State briefly the purpose of the study; usually this will include the hypothesis, which is to be tested.*

Many older adults experience increased difficulty moving about their communities and performing one or more of their basic activities of daily living (ADLs) after undergoing a hospitalization. The purposes of this study are (1) to test the effectiveness of a mobility intervention, compared to usual care, on change in mobility after hospitalization; (2) to determine the impact on one-year outcomes (such as nursing home placement); and (3) to identify which patients benefit the most from the intervention. Ultimately, our goal is to improve recovery after hospitalization and reduce disability in hospitalized patients.

B. BACKGROUND: *Describe past studies and, if relevant, experimental or clinical findings which led to the plan for this project. This must be succinct and comprehensible without extensive reference to other material. A few pertinent references may be cited. In some cases -- e.g., as in cases where earlier studies have produced conflicting evidence -- it will be necessary to cite these studies and explain how it was decided to rely on one side or the other. For studies designed to compare or evaluate therapies, there should be a statement of the relative advantages or disadvantages of alternative modes of therapy. This section should ordinarily be less than one page long; however, when necessary it may be longer.*

Low mobility, defined as mobility limited to bed rest or bed to chair transfers, is common during hospitalization.¹ Our prior work has shown that hospitalized older adults spend greater than 80% of their hospital stay lying in bed and less than 43 minutes per day walking, despite being cognitively intact and able to walk on hospital admission.² Low mobility is associated with adverse outcomes including functional decline, nursing home placement, and death, even after controlling for illness severity and comorbidity.¹ Functional disability after hospitalization is common, and up to one-third of those who experience a decline do not recover.^{1,3} Mobility is a key component of functional disability. Decreases in functional ability are not restricted to older adults; patients in their 5th decade have been shown to experience declines in strength, pulmonary function and submaximal exercise tolerance after five days of hospitalization.⁴ Intervention studies examining the effect of encouraging mobility during hospitalization are sparse and typically measure outcomes in hospital or in the 30 days after discharge.⁵⁻⁷ While data on the long-term impact of a hospital mobility program is lacking, evidence from observational studies reveals that higher levels of hospital mobility are associated with reduced nursing home use and mortality.^{7,8} In our recent VA-funded pilot randomized controlled trial (RCT), we showed that cognitively intact older veterans who received a mobility intervention had higher community mobility, measured with the UAB Life-Space Assessment (LSA), one month after hospital discharge compared with the usual care group.⁹ However, this preliminary work was restricted to one month of follow-up of veterans who were cognitively intact and ≥ 65 years of age. A number of important gaps remain in our understanding of the impact of a hospital mobility program: 1) hospital mobility program studies have not used a randomized controlled trial (RCT) design to evaluate the impact; 2) the actual number of steps and time spent walking by participants has not been measured; 3) outcomes beyond 30 days' post-discharge have not been examined; and 4) characteristics of patients most likely to benefit from this type of intervention have not been identified.

For this high-impact study, we propose to use a stepped wedge cluster randomization design on five VA hospital wards and at UAB Hospital on four hospital wards to compare a mobility program (MP) to usual care (UC) among a cohort of veterans and other patients age ≥ 50 years. We will examine pre- to post-hospital mobility and adverse outcomes including functional decline, nursing home admission, emergency department (ED) visits, hospitalization and death in the mobility program (MP) and usual care (UC) groups in the year after hospital discharge. The primary outcome of mobility will be measured by the UAB Life-Space Assessment (LSA).¹⁰⁻¹³ Secondary measures of mobility will include self-reported ability to walk $\frac{1}{4}$ mile and drive a car, as described by Gill, et al.¹⁴ We will identify patient-specific characteristics that modify the effect of the mobility intervention on post-hospital mobility and adverse outcomes to determine which hospitalized patients are most likely to benefit from this intervention.

C. SPECIFIC LOCATION OF STUDY: Where will the research take place? (When other institutions are involved it may be necessary to secure the approval of their Institutional Review Boards.)

Patients admitted to the medical wards of the BVAMC (4A, 4B, 5A, 5B, and 6B) and to medical wards at UAB Hospital (3 Hospitalist Units, and the Tinsley Harrison service) will be eligible to participate in this study. A brief screening interview will be conducted with the ward team to identify patients who meet eligibility criteria; if eligible, consent to interview the patient will be requested from the physician. Interviews to further determine eligibility and to obtain consent will be conducted in patient rooms. While a participant is hospitalized, study assessments, tests, and interventions will be conducted in patient rooms or, for walking sessions and gait speed assessments, in the hallways of the BVAMC or UAB Hospital. Post-discharge assessments will occur over telephone or, in the rare event that a patient has been re-hospitalized at BVAMC or UAB Hospital, in the participant's hospital room. Telephone assessments will be conducted from rooms 8211, 8223, 8224 and 8218 in the BVAMC. Study staff will conduct these assessments from these private offices with the door closed. Hard copy study records for recruited Birmingham VAMC veterans will be secured in locked file cabinets within locked offices in rooms 8211, 8223, 8224 and 8218 in the BVAMC, with access and key distribution limited to authorized staff. Electronic records will be stored on a VA secure server; only authorized project staff members will have access to the data and the drives/directories on which they are stored. No PHI will be removed from the VA protected environment, nor will any PHI be transmitted electronically. De-identified data sets (data excluding HIPAA identifiers) may be emailed to study statisticians approved by the VA IRB to their UAB email accounts. De-identified data will be stored on secure servers maintained by UAB and accessible solely to study staff on a need-to-know basis. Data sets will be reviewed by the BVAMC Privacy Officer or their representative and will approve all data transfers to UAB. Statisticians will return all analyses to the study PI at BVAMC, and VA data will be deleted from the UAB server when analyses are complete.

Patients admitted to UAB Hospital will also be eligible to participate in this study. Screening and identification of eligible patients will follow the same procedures as at the BVAMC. UAB participants' assessments will occur at UAB; hard copy and electronic records of UAB patients will be stored within UAB facilities as approved by the UAB IRB.

D. PROBABLE DURATION OF PROJECT: This should be the estimate for the entire study. (IRB reapproval is required at least every year as long as the study is continued. In specific cases, more frequent reapproval may be required.)

Active recruitment of participants is expected to last 36 months; all participant assessments are anticipated to be completed in 48 months. Data interpretation and manuscript preparation are anticipated to take two years, for a total estimated study duration of six years.

E. RESEARCH PLAN: This is an orderly description of the intended procedures as they directly affect the subjects. There need not be a detailed account of techniques that do not affect the human subject. Include length of time for various procedures and frequency of repetition, any manipulation that may cause discomfort or inconvenience, and plans for follow-up. If questionnaires or non-standard rating scales are to be used, include copies. (If the rating scale is a standard and familiar one, it is only necessary to name it and no copy need be submitted.)

Statistical considerations: Studies which cannot be expected to answer the questions posed by the research, because of small numbers, low statistical power or other major flaws in research design, can provide no benefit to the subject and cannot justify even the smallest degree of subject inconvenience, let alone risk. Therefore, except for pilot studies, which are clearly designed to further the development of a more extensive research protocol, this section should include a) the number of subjects expected to enter the study, b) a

statement about the statistical power of the study to test the major hypothesis, and c) a summary of the plans for statistical analysis.

Screening, Recruitment & Consent

258 participants, age \geq 50 years admitted for any medical illness (e.g. pneumonia, heart failure, COPD exacerbation, or other medical (versus surgical) indication for hospitalization) to either one of the five medical wards of the Birmingham VAMC, or to one of four units at UAB Hospital, will be recruited within 48 hours of hospitalization, and followed throughout their hospitalization and for 12 months after hospital discharge.

Within 48 hours of admission, patients meeting age and ward criteria for the study will be identified daily (as staffing allows) by reviewing the electronic medical record (EMR). Study staff will then contact the medical physician team assigned to the patient and will conduct a brief screening interview with the team to assure the patient meets inclusion and exclusion criteria.

After speaking with the medical team, study staff will meet with eligible patients in their hospital rooms to briefly inform them about the study and ask if they are interested in hearing more details. If a patient expresses interest, the study will be explained and questions answered. Patients will be told they will be visited three times a day and have several assessments done. They will be informed they will be assigned to either MP or UC depending on their ward assignment. All patients will be informed that they will wear a StepWatch®, which counts the steps they take, and that they will be followed with periodic telephone calls for one year after discharge. If the patient is still agreeable, the Mini-Cog^{15,16} and CAM¹⁷ will be administered to aid in determining the patient's decision-making capacity.

If the patient is deemed cognitively intact based on the Mini-Cog and CAM scores, the consent process will continue. If the patient consents, a brief physical screen will be administered: Patients will be asked if they were able to walk across a small room in the 2 weeks prior to admission, and a progressive functional assessment will be administered in which the patient will be asked to sit and then to stand. If the patient successfully completes the physical screening, the patient will be randomized. If a patient is deemed to be unsafe based on the functional assessment within the 36-hour recruitment window, then a referral to physical therapy will be sought from the physician and the patient will not be randomized nor take part in further study activities.

If the patient scores < 3 on the Mini-Cog or > 0 on the CAM, the consenting individual will consult with the patient's physician. Study staff will inform the physician of the scores, and ask the physician to determine whether the patient has decision-making capacity. If the physician indicates that the patient does indeed have decision-making capacity, the consent process will continue. If the physician deems that the patient does not have decision-making capacity, study staff will ask the physician to enter a EMR note documenting that the patient does not have decision-making capacity, if such a note or document does not already exist in the EMR. Once such documentation has been created or identified in either the EMR or VISTA, study staff will review the EMR and/or Vista to identify the appropriate Legally Authorized Representative (Power of Attorney, Legal Guardian, or Next of Kin). Once identified, the LAR will be contacted in person at the bedside or via the contact information in the electronic records and informed of the study. If the LAR is contacted on the phone, the study will be briefly described and the LAR will be asked if they are interested in hearing more details. If the LAR expresses interest, the study will be more fully explained and questions answered. Consenting staff will ask if the LAR will be physically present in the BVAMC before the patient has been hospitalized for 48 hours (see inclusion/exclusion criteria). If so, consenting staff will attempt to meet with the LAR at the bedside at a time convenient for the LAR. Consenting staff will meet the LAR and the patient, briefly inform them about the study and ask if they are interested in hearing more details. If a patient expresses interest, the study will be explained and questions answered. Patients will be told they will be visited three times a day and have several assessments done. They will be informed they will be assigned to either MP or UC depending on their ward assignment. All patients will be informed that they will wear a StepWatch®, which counts the steps they take, and that they will be followed with periodic telephone calls for one year after discharge. If the patient and LAR are still agreeable, the consent process can continue. If the patient and LAR consent, a brief physical screen will be administered as described above.

If the LAR is first contacted by visiting the patient's room, then consenting staff will describe the study to the LAR and the patient; if both the LAR and the patient express interest, then the screening process will proceed, as described above.

Identification, contacting, and consenting of potential UAB participants' LARs will follow UAB procedures and guidelines.

Figure 1. Screening Flowchart (BVAMC)

[figure not shown]

TABLE 1
Screening Procedures

Procedure	Length of Time Required of Participants	Frequency of Repetition
EMR review	0 minutes (performed by staff)	Once
Screening interview with medical team	0 minutes (performed by staff)	Once
Mini-cog	5 minutes	Once
Confusion Assessment Method (CAM)	<1 minutes	Once
LAR Identification, as necessary	0 minutes (performed by staff)	Once
Ambulation question	<1 minutes	Once
Progressive functional assessment (sit, stand)	5 minutes	Once
Total	<12 minutes	

In-Hospital Procedures

Baseline

Baseline Assessments: After consent, a number of baseline assessments will be administered by study staff using standard testing procedures. These assessments may be administered over two or more sessions: One set of assessments is to be administered on Day 1 of the study and takes a little more than 20 minutes to complete; the second set maybe be completed at any time during hospitalization, and takes about 25 minutes to complete. (See Tables 2 and 3). Study staff will be sensitive to the participant's comfort level, and may postpone or eliminate any assessments if the participant expresses fatigue. Staff will also collect demographic information, as well as contact information for post-discharge assessments.

Depression Assessment: Patients will be administered the Patient Health Questionnaire (PHQ) – 2, which is a 2-question screening tool for depression.¹⁸ Surrogate responses will not be solicited for this assessment. A positive answer to either question is considered a positive screen and will lead the interviewer to complete the PHQ-9.¹⁹ Scores for PHQ-9 range from 0 – 27, with higher scores indicating higher levels of depression. If a patient is noted to have a PHQ-9 ≥ 11 , indicating moderate depression, the patient's BVAMC or UAB physician will be notified by study staff.

TABLE 2
Baseline Assessments, Part 1: to complete on first day in the study

[figure not shown]
Procedure	Length of Time Required of Participants	Frequency of Repetition
Condensed Memorial Symptom Assessment Scale (CMSAS)	5 minutes	Once
Katz ADL	3 minutes	Once
Lawton IADL	3 minutes	Once
UAB Life-Space Assessment	5 minutes	Once
Gait speed	5 minutes	Once
Step count monitoring (via StepWatch)	0 minutes (worn while in hospital)	Continuous during hospitalization
Total	21 minutes	

TABLE 3**Baseline Assessments, Part 2: to complete prior to hospital discharge**

Procedure	Length of Time Required of Participants	Frequency of Repetition
Ability to walk/drive	1 minute	Once
Fall history (previous 4 weeks)	1 minute	Once
ED visit & hospitalization history (previous 6 months)	1-6 minutes	Once
PHQ-2 (& PHQ-9, as appropriate) (depression screening tool)	2 – 6 minutes	Once
Lubben Social Network Scale	7 minutes	Once
EQ-5D-3L (quality of life index)	5 minutes	Once
Total	17-26 minutes	

Mobility Monitoring: The StepWatch® mobility monitor by Modus Health is a small (70 x 50 x 20 mm) waterproof, self-contained accelerometer pedometer that is attached loosely to the ankle via a Velcro strap and captures number of steps taken and when the steps were taken.²⁰ A StepWatch® pedometer will be applied to the ankle and will be worn for the duration of the in-hospital portion of the study by all participants. All patients in the study will wear a StepWatch to allow comparisons of mobility achieved by both the Mobility Program (MP) and Usual Care (UC) groups. Our team has extensive experience with the StepWatches, having used the device in our previous VA Merit study at the BVAMC. Flyers with the study's pager number will be placed on or near the whiteboard located in all patient rooms, and nursing will be informed of the patient's participation in the study and asked to call study staff if there are any questions about the pedometers. The pedometers will be removed as needed if they interfere with routine care, such as MRIs or other procedures.

The StepWatch pedometer is programmed and downloaded with a standard computer via a docking station that plugs into a USB port. The device itself provides no feedback to the patient and **no PHI will be stored on the device**; the only data recorded is the number of steps per minute per day (see Figure 3, sample output from StepWatch). As no PHI is stored on the device, encryption is not necessary. Data cannot be accessed without the docking station and software provided by Modus Health. We have used this hardware and software with no incidents in our previous study at BVAMC (IRB Study ID #01332). For our new study, an updated version of the software will be necessary; the license will be held by the VA, and will be paid for by VA Merit grant funds. All data will be stored on secure server

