and death, we will use Cox proportional hazards models to compare the time from hospital discharge to the time to event between the MP and UC groups, adjusting for potential covariates. Due to the potential interrelationship between risk of nursing home admission and risk of death, competing hazards will be used to model the time to occurrence of the first event. Right censoring of participants will occur with dropout due to any reason (death, loss to follow-up, conclusion of the study period, etc.). Multiple imputation techniques will be used to offset potential bias due to missing predictors in the models.

AIM 2: To identify characteristics which modify the effect of the mobility intervention on recovery to pre-hospital mobility status or better and reduction of adverse outcomes in the year after hospitalization.

Potential effect modifiers include pre-admission ADL and LSA, cognitive function, level of in-hospital mobility, depressive symptoms, and social support. For continuous variables, e.g., activities of daily living score, overall distributions will be reviewed and categorized as low, medium and high based on tertile cut-points. To test for significant effect modification, single second level interaction terms, combining pre-/post-intervention indicators with potential effect modifiers, will be added to mixed models. Resulting F-tests for the interaction terms will be reviewed and p-values <0.05 identified as significant. Examination of potential effect modifiers based upon their tertile groupings not only allows for the identification of significant factors but also has the added benefit of examining factor's dose effect, providing additional internal validity to the analysis.

F. ECONOMIC CONSIDERATIONS: *Describe any material inducements that will be offered to subjects in return for their participation: e.g., direct payment, free services, etc. Describe any schedule of payment to subjects based on their complete or partial participation. Will early withdrawal from the study result in a reduced payment? Does it make a difference whether it is the subject or the investigator who decides to terminate the subject's participation? Explain any bonus a subject may receive for completion of the study. These partial or bonus payments must also be explained in the consent form.*

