Data Safety and Monitoring Board (DSMB) The Data Safety and Monitoring Board will be charged with recommending changes in the study protocol or closure of the study if the incidence of falls or another adverse event in the intervention group at BVAMC is significantly greater than that observed in the control group at BVAMC. The board's membership will include a physician, a physical therapist and a nurse. The DSMB will meet quarterly either in-person or by conference call to discuss the study and any issues or concerns. Incidents will be reported to the DSMB by email.

The following incidents which occur at BVAMC will be reported to the DSMB and IRB immediately:

1. Falls by participants that occur during the inpatient portion of the study
2. Open wounds (Stage II or greater pressure ulcers indicating a breach of the skin's integrity) under the area of the StepWatch

The following incidents which occur at BVAMC will be reported to the DSMB quarterly:

1. Falls by participants that occur after the inpatient portion of the study, but while enrolled, together with statistics on the current fall rate at BVAMC
2. Participants' deaths that occur after the inpatient portion of the study, but while enrolled
3. Emergency department visits that occur after the inpatient portion of the study, but while enrolled
4. Rehospitalizations that occur after the inpatient portion of the study, but while enrolled
5. Participant transferred to ICU/CCU or Safe Harbor during the inpatient portion of the study
6. Participant dies during the inpatient portion of the study
7. Skin irritation in the immediate vicinity of the StepWatch

AEs, SAEs, and other incidents which involve UAB participants will be reported to the UAB IRB.

K. POTENTIAL BENEFITS: Assess the potential benefits to be gained by the individual subject, as well as benefits which may accrue to society in general as a result of the planned work.

For the group of patients who receive the hospital mobility intervention, it is expected they will maintain or improve their mobility to a greater degree than those in the usual care group. As ability to walk is a key component of all basic activities of daily living, the MP group may also experience an improvement in their ADL ability to a greater degree after hospital discharge. As mobility disability is associated with a reduction in quality of life, the MP group may experience an improvement in quality of life.

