It is expected that there will be little direct benefit to those participants who are randomized to the control group. However, they will be visited three times a day for social visits, which may increase their feeling of wellbeing.

L. THE RISK-BENEFIT RATIO: This section should consist of the investigator's explanation of how he or she concluded that the risks to subjects are reasonable in relation to anticipated benefits, if any, to subjects, and the importance of the knowledge that may reasonably be expected to result.

The risks to the subjects are very small, whereas the results of this study will add substantively to what is currently known about how to improve outcomes due to low mobility for middle-aged and older adults who have a hospitalization. Functional decline, loss of mobility, and nursing home admission are well-recognized negative outcomes associated with hospitalization, and available evidence suggests low mobility to be a contributor to these adverse outcomes; determining the effectiveness of a hospital mobility program could have significant impact on functional decline and loss of mobility for hospitalized patients. The potential benefits are great if the study allows for the development of a hospital mobility program intervention that could ultimately decrease loss of mobility and functional decline and reduce ED visits, hospitalizations and the need for nursing home care after hospitalization.

References:

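### Baseline Part 2, including the PHQ and Lubben scale, may be completed any time before discharge, so two Aim 2 effect modifiers (mainly depressive symptoms) can be measured after exposure to the assigned condition

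*Protocol*

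**What the plan says.** Protocol Section E (In-Hospital Procedures, Baseline) splits the baseline battery in two.

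- **Part 1:** "One set of assessments is to be administered on Day 1 of the study". Table 2 lists the symptom scale, Katz ADL, Lawton IADL, LSA and gait speed, plus the step monitor.
- **Part 2:** "the second set maybe be completed at any time during hospitalization, and takes about 25 minutes to complete". Table 3 is headed "Baseline Assessments, Part 2: to complete prior to hospital discharge" and lists the walk/drive item, fall history, ED and hospitalization history, PHQ-2/9, Lubben scale and EQ-5D-3L.

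Staff "may postpone or eliminate any assessments if the participant expresses fatigue".

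Under Daily visits, MP sessions and UC friendly visits are each offered up to three times daily throughout the stay, as staffing allows. No sentence places either part of the baseline before the first of these contacts.

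For Aim 2, the protocol states: "Potential effect modifiers include pre-admission ADL and LSA, cognitive function, level of in-hospital mobility, depressive symptoms, and social support". The SAP gives the same list. In both, continuous modifiers are cut at tertiles of the overall distribution and tested as interactions with the pre-/post-intervention indicator. Only ADL and LSA are labelled as pre-admission. Neither document limits Aim 2 to modifier values obtained before exposure.

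**The concern.** An effect modifier should be fixed before treatment can act on it. Otherwise the subgroups are partly formed by treatment, and comparing MP with UC inside a tertile no longer compares like with like. The plan accepts this principle in Aim 1, where covariates are adjusted for only if they are not judged to result from the intervention. Aim 2 has no matching safeguard.

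Depressive symptoms and social support are evidently meant as patient characteristics present at entry, yet the timing rule lets both be recorded as late as the day of discharge. Timing could also differ by arm: assessments may be put off for fatigue, and Section H names fatigue as a possible effect of walking during tests or mobility sessions. What is at stake is the study's third stated purpose, identifying which patients benefit most, for two of the six listed modifiers.

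**Working it through.** No stated figure is in dispute. The check sets the timing rules beside the analysis, then asks how much could follow.

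**1. Where each Aim 2 modifier is measured in hospital**

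| Modifier | Source | Timing rule |
|---|---|---|
| Pre-admission ADL, LSA | Table 2 (Part 1) | Day 1 |
| Cognitive function | Screening (Table 1) | Before enrolment |
| Level of in-hospital mobility | Step monitor | During the stay, by definition (a separate matter) |
| Depressive symptoms | PHQ-2/9, Table 3 (Part 2) | Any time to discharge |
| Social support | Lubben, Table 3 (Part 2) | Any time to discharge |

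**2. How many contacts can precede Part 2**

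If contacts start on study day 1 at the maximum rate, the ceiling before the start of day d is 3 × (d − 1):
- day 2: 3
- day 3: 6
- day 5: 12

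The days are assumptions, because length of stay is not given. Sessions may be refused and depend on staffing, so these are upper limits.

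**3. Minutes involved**

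- Part 1 as printed: 5 + 3 + 3 + 5 + 5 = 21.
- Part 2 as printed: low 1 + 1 + 1 + 2 + 7 + 5 = 17; high 1 + 1 + 6 + 6 + 7 + 5 = 26. Both table totals agree with the protocol.
- PHQ moved: Part 1 becomes 21 + 2 to 21 + 6 = 23–27.
- PHQ and walk/drive moved (3–7 minutes): 24–28.
- PHQ, Lubben, walk/drive and EQ-5D all moved (15–19 minutes): 36–40.

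**4. Could late measurement create a false gradient?**

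This is an illustration with assumed inputs, not an estimate for this trial. There are 400,000 simulated patients, allocated 1:1, with no clustering or repeated measures. U is the pre-treatment modifier (standard normal), r an individual response (standard normal) and T = 1 for MP.

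- Measured modifier: M = U − T × (s + h × r)
- LSA: Y = 50 − 4U + T × (10 + b × r) + error (SD 20)

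The true effect is 10 points in every tertile of U. Effects by tertile of M, low to high:

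| s | h | b | MP minus UC |
|---|---|---|---|
| 0 | 0 | 0 | 9.9 / 9.9 / 10.1 |
| 0.2 | 0 | 0 | 9.4 / 9.2 / 9.4 |
| 0.3 | 0.3 | 5 | 10.1 / 8.6 / 7.7 |
| 0.2 | 0.5 | 5 | 11.1 / 9.3 / 7.6 |
| 0.3 | 0.5 | 8 | 12.1 / 8.6 / 5.8 |

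With no shift there is no bias. A uniform shift gives mild attenuation and no gradient. A spurious gradient appears when the individual shift in the modifier also tracks LSA benefit. The documents give no values for s, h or b, and without recorded timing the analysis could not tell which row applies.

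**The case against.** The case on the other side is substantial, and it limits the point in several ways.

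- **Late timing is allowed, not planned.** Part 2 may equally be done on Day 1. Splitting the battery is a deliberate concession to acutely ill patients. This stands, and it argues against moving the whole set.
- **Section K might be read as saying that both conditions will move these scores.** It does not. It says that "the MP group may experience an improvement in quality of life" and, of UC patients, that "they will be visited three times a day for social visits, which may increase their feeling of wellbeing". Both are possibilities, and neither names depression or social network.
- **Social support is unlikely to change in a short stay.** Tables 8 and 9 repeat the full Lubben scale only at months 6 and 12, with a change question at months 3 and 9, so the protocol appears to treat it as slow-moving. The point therefore weighs mainly on the PHQ.
- **A reader might infer that the secondary outcomes are distorted**, because the item "Ability to walk/drive" is also in Part 2. The planned GLMMs compare periods and name no baseline or change score for walking or driving. The recall period is not stated either; if the item asks about ability before admission, sessions cannot alter the true answer. Its baseline matters only if change or recovery in these items is analysed. EQ-5D enters no stated analysis.
- **Bias is possible, not shown.** The gradient above needs assumed responses.

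What remains is that nothing in either document prevents or detects a modifier measured after exposure.

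**Conclusion.** The point holds for Aim 2. Under full compliance, two of six listed modifiers can be measured after sessions or visits have begun, in either arm and in any of the 258 participants. The practical concern is the PHQ. Whether bias follows depends on two things that the documents do not give: how late Part 2 is done, and whether the assigned condition shifts the score. Size and direction are therefore unknown, and the simulated gradients must not be read as expected values.

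It would be tempting to extend this to the primary result. The documents do not support that, since the LSA baseline is in Part 1 on Day 1. Part 1 is not explicitly placed before the first contact, and one added sentence would settle this.

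**What to change.** **Collection** (Section E, Baseline; Tables 2 and 3)

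- Move the PHQ-2/9 to Part 1 and, if feasible, the 1-minute walk/drive item.
- State that Part 1 precedes the first session or friendly visit.
- Record the date and time of every Part 2 item.

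**Analysis** (Aim 2, protocol and SAP)

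- Report by arm when Part 2 was done relative to the first session or visit.
- Add a sensitivity analysis limited to PHQ and Lubben values taken before the first session or visit. Later values stay in the main analysis; discarding them all would lose observed data, probably more often from fatigued patients.

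**If enrolment has ended.** The ward schedules in Figures 4 and 4A finish on 12/31/19 and the protocol is dated February 5, 2021, so this is likely. Then apply only the analysis part where assessment dates exist. Where they do not, report the depression and social-support modifier results as possibly post-treatment.

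**Cost.** About 2–7 more minutes before the first visit, offset by an equally shorter Part 2 (15–20 minutes with the PHQ moved, 14–19 with both items moved). There will be some deferred values in fatigued patients, a time field on the form, and a smaller sample in the sensitivity analysis.
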